## 10.2 Adverse Event Definitions

**Adverse Event:** Adverse event means any untoward medical occurrence associated with the use of a drug in humans, whether or not considered drug related. An adverse event can be any unfavorable and unintended sign (eg, an abnormal laboratory finding), symptom, or disease temporally associated with the use of a drug, without any judgment about causality.

**Adverse Reaction:** Adverse reaction means any adverse event definitely caused by the drug.

**Suspected Adverse Reaction:** Suspected adverse reaction means any adverse event for which there is a "reasonable possibility" (ie, evidence indefinite but suggests a causal relationship between the drug and the adverse event) that the drug caused the adverse event. By definition, a suspected adverse reaction is identical to the definition of adverse drug reaction per ICH E2A.

Examples that would suggest a causal relationship:

- A single occurrence of an event that is uncommon and known to be strongly associated with drug exposure (eg, angioedema, hepatic injury, Stevens-Johnson Syndrome)
- One or more occurrences of an event that is not commonly associated with drug exposure, but is otherwise uncommon in the population exposed to the drug (eg, tendon rupture)
- An aggregate analysis of specific events observed in a clinical trial (eg, known consequences of the underlying disease or condition under investigation or other events that commonly occur in the study population independent of drug therapy) that indicates those events occur more frequently in the drug treatment group than in a concurrent or historical control group.

**Unexpected Adverse Event or Unexpected Adverse Reaction:** An adverse event or adverse reaction is considered “unexpected” if it is not listed in the Investigator’s Brochure or is not listed at the specificity or severity that has been observed.

Adverse events or adverse reactions that are mentioned as occurring with a class of drugs or as anticipated from the pharmacological properties of the drug will be considered “unexpected” if they are not specifically mentioned as occurring with the particular drug under investigation.

Until the Investigator’s Brochure is updated to include a new serious suspected adverse reaction, subsequent occurrences of similar serious suspected adverse reactions must be submitted expeditiously to FDA in Investigational New Drug (IND) Safety Reports and to other appropriate regulatory authorities in countries other than the United States in an Individual Case Safety Report (ICRS) or using a Council for International Organizations of Medical Sciences I form, as appropriate.

**Serious Adverse Event or Serious Adverse Reaction:** An adverse event or adverse reaction is considered “serious” if, in the view of either the Investigator or Sponsor, it results in any of the following outcomes:

- Death
- A life-threatening adverse event
- Inpatient hospitalization or prolongation of existing hospitalization
- A persistent or significant incapacity or substantial disruption of the ability to conduct normal life functions
- A congenital anomaly/birth defect.

Important medical events that may not result in death, be life-threatening, or require hospitalization may be considered serious when, based upon appropriate medical judgment, they may jeopardize the subject and may require medical or surgical intervention to prevent one of the outcomes listed in this definition.

If either the Investigator or Sponsor believes that the event is serious, it must be evaluated by the Sponsor for expedited reporting to regulatory authorities.

**Life-Threatening Adverse Event or Life-Threatening Adverse Reaction:** An adverse event or suspected adverse reaction is considered “life-threatening” if, in the view of either the Investigator or the Sponsor, its occurrence places the subject at immediate risk of death.

**Serious Unexpected Suspected Adverse Reaction:** An adverse event for which there is a reasonable possibility that the drug caused the adverse event, and it is not listed in the Investigator’s Brochure or is not listed at the specificity or severity that has been observed, and it results in any of the serious outcomes listed above. This criterion is consistent with the concepts of FDA 21 Code of Federal Regulation (CFR) 312 and the ICH E2A Guideline for expedited safety reports.

The Sponsor must notify the appropriate regulatory authority(ies) and all participating Investigators in an expedited safety report (eg, IND Safety Report or ICRS) of potentially serious risks from clinical trials or any other source (ie, a serious unexpected suspected adverse reaction), as soon as possible, but no later than 15 calendar days after the Sponsor receives the safety information and determines that the information qualifies for reporting.

During the course of drug development, the Sponsor may become aware of new safety information from a variety of sources and will decide if an individual case of a serious and unexpected adverse event meets the criteria for reporting to regulatory authorities.

If the adverse event does not meet all criteria (ie, reasonable possibility of causality, serious and unexpected), it should not be submitted as an expedited safety report.

Any unexpected fatal or life-threatening suspected adverse reaction must be reported to regulatory authorities no later than 7 calendar days after the Sponsor receives the safety information.

### **10.3 Assessment of Relationship to Study Drug**

The following criteria must be used to by the Investigator to characterize the relationship or association of study drug in causing or contributing to the adverse event:

**Unrelated:** Relationship suggests no association of the event to study drug; the event is related to other etiologies, such as the subject’s clinical state or concomitant medications

**Unlikely:** Relationship suggests an unlikely association of the event to study drug given the subject’s current disease state

**Possible:** Relationship suggests treatment with study drug caused or contributed to the event; the event follows a reasonable temporal sequence from administration of study drug and/or follows a known response pattern to the study drug; the event might have been produced by other factors (eg, the subject’s clinical state or other modes of therapy administered to the subject)

**Related:** Relationship suggests a definite causal relationship to study drug; the event follows a known response pattern to the study drug and cannot be reasonably explained

by the known characteristics of the subject's clinical state or other modes of therapy administered to the subject

#### **10.4 Assessment of Severity**

The following criteria must be used by the Investigator to rate the intensity of the adverse event:

**Mild:** Awareness of signs or symptoms, but easily tolerated and are of minor irritant type causing no loss of time from normal activities; symptoms do not require therapy or a medical evaluation; signs and symptoms are transient

**Moderate:** Events introduce a low level of inconvenience or concern to the subject and may interfere with daily activities, but are usually improved by simple therapeutic measures; moderate experiences may cause some interference with functioning

**Severe:** Events interrupt the subject's normal daily activities and generally require systemic drug therapy or other treatment; they are usually incapacitating

#### **10.5 Breaking the Blind**

Not applicable as this is an open-label study.

### **11 STATISTICAL CONSIDERATIONS**

This section outlines the nature and rationale for the statistical methods to be used for the study design and analysis. A separate Statistical Analysis Plan will describe data handling and statistical techniques in full detail.

#### **11.1 Endpoints**

The following efficacy endpoints are defined for the study.

Primary Endpoint: Percentage of subjects in each treatment group in categories 4 through 8 of the 8-point WHO Ordinal Clinical Scale through Day 28.

Secondary Endpoints:

- Time to first occurrence of either death from any cause or new/worsened organ dysfunction through Day 28, defined as at least one of the following:
  - Respiratory decompensation
  - New or worsening congestive heart failure
  - Requirement of vasopressor therapy and/or inotropic or mechanical circulatory support
  - Ventricular tachycardia or fibrillation lasting at least 30 seconds and/or associated with hemodynamic instability or pulseless electrical activity, or resuscitated cardiac arrest

- Initiation of renal replacement therapy.
- Percentage of subjects who are alive at Day 28.
- Among subjects who begin oxygen therapy, mean change from initiation to last day on oxygen or Day 28 (whichever happens first) in SpO2/FiO2 ratio.
- Percentage of subjects with fever through Day 28.
- Percentage of subjects who develop AKI, as determined by the Investigator, through Day 28.
- Percentage of subjects with new or worsening congestive HF through Day 28.
- Percentage of subjects with ventricular tachycardia or fibrillation lasting at least 30 seconds and/or associated with hemodynamic instability or pulseless electrical activity, or resuscitated cardiac arrest through Day 28.
- Percentage of subjects who remain hospitalized at Day 28.
- Length of hospitalization through Day 28.
- Number of oxygen-free days through Day 28.
- Percentage of subjects transferred to the ICU through Day 28.
- Number of days on mechanical ventilation through Day 28.
- Time to and duration of vasopressor or inotrope utilization through Day 28.
- Percentage of subjects who begin dialysis through Day 28.

Exploratory Endpoints:

- Duration of COVID-19 symptoms through Day 56

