**Statistics continued:**

**Efficacy Analysis:** The primary efficacy endpoint will be analyzed using a 2-sided Fisher Exact test and a logistic regression model to control for the stratification factor (time since COVID-19 diagnosis); the method of Firth will be used to predict outcomes. A 2-sided Wilcoxon rank sum test will be used to compare the distributions of scores on the 8-point WHO Ordinal Clinical Scale for the 2 treatment groups. Continuous endpoints will be evaluated using a mixed model repeated measures analysis using a compound symmetry error structure. Time to event outcomes (e.g., extubation, hospital discharge, death) will be displayed using a Kaplan-Meier life table and treatment distributions compared using a stratified log-rank test and Cox proportional hazards model to control for time since diagnosis and treatment including the interaction term. A Greenwood test will be performed using the Day 28 estimates from the Kaplan-Meier lifetable.

**Safety Analysis:** Safety measures including adverse events, clinical laboratory tests, vital signs, physical examinations, and concomitant medication usage will be summarized descriptively by treatment group.

When appropriate, summary statistics will be provided (number of non-missing values, mean, median, standard deviation, minimum, and maximum for continuous variables and number and percentage of patients for categorical variables) by treatment group for all measures, including demographic and baseline assessments, safety, and efficacy endpoints. Baseline for all safety and efficacy endpoints is defined as the last observations before administration of study drug. No imputation will be used for missing data.

**Interim Analyses:** A group sequential design will be conducted with 4 pre-planned interim analyses after 30, 60, and 90 subjects complete the Day 7 evaluation and 150 subjects complete the Day 28 evaluation. At each interim, the DSMB will evaluate an independently conducted analysis in order to assess safety and futility.

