- 6 Severity of COVID-19 will be assessed by the 8-point WHO Ordinal Clinical Scale, which includes: 1. Ambulatory (not hospitalized), no limitation of activities; 2. Ambulatory (not hospitalized), limitation of activities; 3. Hospitalized, no oxygen therapy; 4. Hospitalized, oxygen by mask or nasal prongs; 5. Hospitalized, non-invasive ventilation or high-flow oxygen; 6. Hospitalized, intubation and mechanical ventilation; 7. Hospitalized, ventilation plus additional organ support – vasopressors (pressors), renal replacement therapy (RRT), extracorporeal membrane oxygenation (ECMO); 8. Death. The Ordinal Clinical Scale is the clinical status at the first assessment of a given study day.
- 7 Parameters include: total protein, albumin, bicarbonate, blood urea nitrogen, serum creatinine, total bilirubin, alkaline phosphatase, glucose, sodium, potassium, phosphorus, calcium, magnesium, gamma-glutamyl transferase, alanine aminotransferase, aspartate aminotransferase, and ferritin.
- 8 Clinical chemistry and hematology are optional on Day 28.
- 9 Parameters include: hemoglobin, hematocrit, leukocytes with differential (absolute), and platelets.
- 10 Parameters include pH, specific gravity, protein, glucose, nitrite, ketones, WBC esterase, and occult blood.
- 11 Administer study drug after all pre-dose evaluations have been completed.
- 12 Adverse events that are ongoing on Day 28 will be followed on Day 42; adverse events that are ongoing on Day 42 will be followed on Day 56.
- 13 Safety follow-up assessment will be conducted virtually by telephone or video contact to determine the following: hospitalization status (hospitalized: yes, no), intubation status (intubated: yes, no), and survival (alive: yes, no).

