#### Risk Factors

- Documented history of coronary artery disease
- Heart failure (New York Heart Association Class 3 or 4)
- Documented history of stroke
- Chronic lung disease (eg, asthma or chronic obstructive pulmonary disease) requiring treatment
- Diabetes mellitus, requiring at least 1 prescription medicine for management
- Documented CKD with an estimated glomerular filtration rate  $<30$  mL/min, not on dialysis
- Obesity (Class 2 or 3; body mass index  $>34.9$  kg/m^2)
- On immunosuppressive therapy
- Oxygen saturation between 90 and 95% with or without supplemental oxygen

4. Admitted to a hospital (or controlled facility such as an emergency room, urgent care facility, temporary/modular hospital, infusion center, clinical research unit, etc; hereafter referred to as hospital) for observation and/or treatment
5. If female, must be postmenopausal, surgically sterile, or if of childbearing potential, must be practicing 2 effective methods of birth control during the study and through 30 days after completion of the study.
6. For females of childbearing potential, a urine pregnancy test must be negative at the Screening Visit.
7. If male, must be surgically sterile or willing to practice 2 effective methods of birth control during the study and through 30 days after completion of the study.
8. Must be willing and able to give informed consent and comply with all study procedures.

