## **9.2 Exclusion Criteria**

Subjects will be ineligible for study participation if they meet any of the following criteria:

1. Anticipated need for ICU care and/or ventilatory support (invasive or non-invasive) within 24 hours.
2. Evidence of acute cardiac injury, as determined by the Investigator at the time of Screening. This may be based upon clinical signs and symptoms, ECG findings, or elevated troponin I.
3. Evidence of acute kidney injury not due to pre-renal azotemia or urinary tract obstruction at the time of Screening.
4. Oxygen saturation <90% on supplemental oxygen with a nasal cannula, including high-flow oxygen.
5. Requires non-invasive ventilation at the time of Screening.
6. Requires dialysis at the time of Screening.
7. Has received or is receiving anti-IL-6 therapies (eg, Tocilizumab, Sarilumab, Silituximab, etc) for the treatment of COVID-19; subjects receiving anti-IL-6 therapies for underlying medical conditions that are unrelated to COVID-19 are not excluded from eligibility.
8. Pregnant or lactating.
9. History of photosensitivity or active skin disease that, in the opinion of the Investigator, could be worsened by RBT-9.
10. Known hypersensitivity or previous anaphylaxis to RBT-9 (stannous protoporphyrin) or any tin-based product.
11. Treatment with an investigational drug or participation in an interventional trial within 30 days prior to treatment with study drug.
12. Has received COVID-19 vaccination.

13. Has received anti-SARS-CoV-2 antibody therapy.
14. Inability to comply with the requirements of the study protocol.

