## 9.7 Study Phase

### 9.7.1 Screening (Within 24 Hours Prior to Dosing)

Study candidates will be evaluated for study entry according to the stated inclusion and exclusion criteria ([Sections 9.1](#) and [9.2](#), respectively). The following procedures will be performed during Screening to establish each candidate's eligibility for enrollment into the study:

- Obtain signed, written informed consent. The informed consent must be signed before any procedures are performed.
- Record demographic information. The subject should also provide phone/email information for themselves and their closest relative so they can be contacted for virtual visits.
- Record medical history, including documentation of COVID-19 infection.
- Record COVID-19 signs and symptoms.
- Record concomitant medications, including previous treatment with anti-IL-6 therapies or Remdesivir.
- Perform physical examination, including calculation of body mass index.
- Record vital signs (blood pressure, pulse rate, SpO2, FiO2, and temperature).
- Obtain urine sample for pregnancy testing for female subjects of childbearing potential.
- Obtain blood samples for clinical chemistry, hematology, and troponin I testing.
- Obtain urine sample for urinalysis.
- Assess the severity of COVID-19 using the 8-point WHO Ordinal Clinical Scale (see [Section 9.10.5](#)).

The Investigator will evaluate the results of all examinations, including clinical laboratory tests, and determine each candidate's suitability for the study according to the eligibility criteria.

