#### **9.10.7 Severity of COVID-19 (8-Point WHO Ordinal Clinical Scale)**

The severity of COVID-19 will be assessed using the following 8-point WHO Ordinal Clinical Scale at the timepoints defined in [Section 5.1](#). The scale measures the clinical status of a subject at the first assessment of a given day.

- 1) Ambulatory (not hospitalized), no limitation of activities;
- 2) Ambulatory (not hospitalized), limitation of activities;
- 3) Hospitalized, no oxygen therapy;
- 4) Hospitalized, oxygen by mask or nasal prongs;
- 5) Hospitalized, non-invasive ventilation or high-flow oxygen;
- 6) Hospitalized, intubation and mechanical ventilation;
- 7) Hospitalized, ventilation plus additional organ support – vasopressors (pressors), renal replacement therapy (RRT), extracorporeal membrane oxygenation (ECMO);
- 8) Death.

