## 11.3 Data Analysis

The primary efficacy endpoint will be mapped to a binary endpoint (% categories 4-8) and then will be analyzed using a two-sided Fisher Exact test and using a logistic regression model to control for the stratification factors; the method of Firth will be used to predict outcomes. A two-sided Wilcoxon rank sum test will be used to compare the primary efficacy endpoint distributions for the two treatment groups. Continuous endpoints will be evaluated using a mixed model repeated measures (MMRM) analysis using a compound symmetry (CS) error structure. Time to event outcomes (eg, extubation, WHO progression, death) will be displayed using a Kaplan-Meier (KM) lifetable and treatment distributions compared using a stratified log-rank test and Cox proportional hazards model to control for time since COVID-19 diagnosis.

When appropriate, summary statistics will be provided (number of non-missing values, mean, median, standard deviation, minimum, and maximum for continuous variables and number and percentage of patients for categorical variables) by treatment group for all measures, including demographic and baseline assessments, safety, and efficacy endpoints. Baseline for all safety and efficacy endpoints is defined as the last observations before administration of study drug. No imputation will be used for missing data.

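### The primary analysis ignores baseline ordinal category, although subjects on oxygen can enter already in a failure category, and no rule says which visits define failure

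*Combined protocol and SAP*

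**What the plan says.** **Endpoint.** Section 11.1 and the synopsis give "Percentage of subjects in each treatment group in categories 4 through 8 of the 8-point WHO Ordinal Clinical Scale through Day 28". Section 11.3 maps this to a binary variable. Neither says whether failure means Day 28 status, the worst score after baseline, or any score recorded.

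**Eligibility.** One of the nine risk factors in section 9.1 is "Oxygen saturation between 90 and 95% with or without supplemental oxygen". Section 9.2 excludes "Oxygen saturation <90% on supplemental oxygen with a nasal cannula, including high-flow oxygen", but not oxygen use as such. Category 4 in section 9.10.7 is "Hospitalized, oxygen by mask or nasal prongs", where failure begins.

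**Analysis.** Section 11.3 plans Fisher's exact test and "using a logistic regression model to control for the stratification factors", with Firth's method. The synopsis names a single factor: "a logistic regression model to control for the stratification factor (time since COVID-19 diagnosis"). Section 9.3 stratifies by that factor alone.

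**Baseline data.** Section 9.7.1 lists, at Screening, "Assess the severity of COVID-19 using the 8-point WHO Ordinal Clinical Scale". Section 11.3 defines baseline as the last observation before dosing, but no rule connects the baseline category to the primary endpoint.

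**Timing.** Footnote 6 of section 5.1 says "The Ordinal Clinical Scale is the clinical status at the first assessment of a given study day", while section 9.7.3 lists a post-dose severity record on Day 1. Section 11.7 places the looks at 30, 60 and 90 subjects after Day 7 data and the look at 150 after Day 28 data.

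**The concern.** A subject on mask or prong oxygen at entry is already in category 4. One on high-flow oxygen with saturation of at least 90% is in category 5 and is not clearly excluded. The visit rule decides whether such a subject can ever be a non-failure. If failure is the worst post-dose score and Day 1 counts, anyone still on oxygen at the Day 1 assessment fails in either arm, whatever the drug does. If only later visits or Day 28 status count, recovery is possible.

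The wording does not settle this. Section 11.1 separates outcomes through Day 28 from outcomes at Day 28, which suggests an interval, while section 7.1 speaks of clinical status. Day 1 is doubtful too, because the first assessment of that day may precede dosing. The Day 7 looks use the same categories with no stated link to the final endpoint.

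Baseline category is likely to predict strongly an outcome that starts at category 4, so leaving it out can give up power for nothing in return. Treatment is open-label (sections 9.6 and 10.5), so the visit rule should be fixed before outcomes are seen. Section 11.6 applies its rates to all 252 subjects without saying how those on oxygen were counted.

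**Working it through.** **Inputs from section 11.6.** n1 = 84 placebo, n2 = 168 RBT-9, two-sided alpha 0.045, failure rates 25 v 10%, 32 v 15% and 38 v 20%. **Assumed:** the share f on oxygen at entry (5-20% unless stated), and a 50/50 split of the time stratum in simulations. Firth models use the penalised likelihood ratio test, with 4,000 simulations per cell; the simulation standard error near 85% is √(0.85 × 0.15/4,000) = 0.6 points.

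**1. The plan's own figure.** With pooled rate p̄, power = Φ{[p1 − p2 − z√(p̄(1−p̄)(1/n1+1/n2))] / √(p1(1−p1)/n1 + p2(1−p2)/n2)}, z = 2.005. For 25 v 10%: p̄ = 0.15, so (0.150 − 2.005 × 0.0477)/0.0526 = 1.03, power 84.9%. The other pairs give 85.6% and 84.6%. The table's 84, 85 and 84% reproduce. Exact Fisher power is 83.6, 84.0 and 82.5%.

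**2. Scenario A: every on-oxygen subject fails and the planning rates describe only the others.** The overall rate is P = f + (1 − f)p. For 25 v 10% at f = 10%: 0.10 + 0.90 × 0.25 = 0.325 and 0.10 + 0.90 × 0.10 = 0.190; p̄ = 0.235, so (0.135 − 2.005 × 0.0567)/0.0594 = 0.36, power 64.1%. Power (%) for the three pairs in order:

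| f | Chi-square | Exact Fisher | Firth, planned | Firth plus baseline oxygen |
|---|---|---|---|---|
| 5% | 74.4, 77.7, 78.0 | 71.5, 75.2, 75.1 | 73.5, 78.0, 77.6 | 82.9, 84.3, 82.4 |
| 10% | 64.1, 69.6, 71.0 | 61.0, 66.1, 68.1 | 62.9, 68.8, 71.7 | 81.1, 81.7, 81.3 |
| 20% | 46.9, 54.3, 57.4 | 43.4, 51.6, 56.0 | 45.7, 53.0, 56.9 | 76.6, 76.6, 75.3 |

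**3. Scenario B: every on-oxygen subject fails, but the planning rates are overall rates.** This is the ordinary reading of section 11.6. Unadjusted power stays about 85%, but the off-oxygen rates must be (p − f)/(1 − f):

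| f | Off-oxygen failure, placebo v RBT-9 | Relative reduction needed |
|---|---|---|
| 0 | 25 v 10, 32 v 15, 38 v 20% | 60, 53, 47% |
| 5% | 21.1 v 5.3, 28.4 v 10.5, 34.7 v 15.8% | 75, 63, 55% |
| 10% | 16.7 v 0, 24.4 v 5.6, 31.1 v 11.1% | 100, 77, 64% |

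**4. Scenario C: only Days 7-28 count, and 30-70% of on-oxygen placebo subjects fail (assumed); planning rates describe the others.** Firth power:

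| Drug effect in on-oxygen subjects | f | Planned | Plus baseline oxygen |
|---|---|---|---|
| Same odds ratio | 10% | 83.8-87.4% | 83.7-87.9% |
| Same odds ratio | 20% | 83.1-87.5% | 83.1-89.7% |
| None | 10% | 67.5-76.3% | 73.7-77.2% |
| None | 20% | 52.9-65.4% | 61.2-66.6% |

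**5. Scenario D: planning rates are overall rates and on-oxygen subjects can avoid failure, f = 10-40%.** This also covers Day 28 status.

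| Odds of failure, on v off oxygen (assumed) | Planned | Plus baseline oxygen |
|---|---|---|
| 1 | 84.2-86.4% | 83.9-86.0% |
| 3 | 83.7-86.0% | 84.5-87.1% |
| 6 | 84.0-87.0% | 86.8-90.2% |

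The largest loss from adjusting in the simulated scenarios was 0.5 points, within simulation error.

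**6. Type I error** (10,000 simulations, nominal 0.045): Fisher 0.036-0.044; Firth with oxygen 0.041-0.048.

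**The case against.** Omitting a baseline covariate from a randomised comparison causes no bias and no inflation of type I error, and Fisher's test with a stratification-adjusted model is a legitimate choice. That stands: this is a point about efficiency and clarity.

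The large losses in scenario A need several assumptions together: a worst-score rule, Day 1 counting, every on-oxygen subject failing, and planning rates that exclude those subjects. No text supports the last. The share on oxygen appears nowhere and may be small, since section 6.2 aims at early disease. The 100% reduction in scenario B comes from one pair at one value of f. All this stands, and scenario A is a bound rather than a forecast.

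Section 11 leaves data handling to a separate Statistical Analysis Plan, which is not in the supplied text and may contain the visit rule. That limits what can be said about the visit rule. It does less for the covariates, which the protocol already lists without baseline category.

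Other planned analyses touch on worsening (organ dysfunction, WHO progression, oxygen-free days, the Wilcoxon test), but none adjusts the primary test.

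Using the adjusted model at small looks could also be questioned: at 60 subjects and f = 5% about 3 are on oxygen, and the chance of none among 20 placebo subjects is 0.95^20 = 36%. Simulated Firth type I error at n = 60 and 90 was nevertheless 0.036-0.050 against a nominal 0.045. That check was not made at the interim alphas of 0.001 and 0.002.

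**Conclusion.** The concern holds. On the supplied text, subjects can enter in a failure category, the stated primary analysis ignores that category although it is collected, and no rule says which visits make a failure. It should be fixed, but it does not invalidate the design.

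The size depends on two things the documents do not give: the share on oxygen at entry and the visit rule. In the worst reading, planned power is 74-78% at a 5% share and 46-57% at 20%, and adjustment brings it to 82-84% and 75-77%. With overall planning rates and all on-oxygen subjects failing, power holds only if the effect in the others is larger than the table shows: a 55-75% relative reduction at a 5% share, against 47-60% with none on oxygen. In milder readings with a common effect there is no real loss, and adjustment changes power by between −0.5 and about +5 points. If the drug does nothing in on-oxygen subjects, adjustment helps but does not restore the planned power. The case for adjusting rests on this asymmetry: material protection in some readings and almost no cost in the rest.

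**What to change.** 1. Add the Screening ordinal category, or baseline oxygen use (yes/no), to the planned Firth model alongside time since diagnosis. The simulations tested the yes/no form. Name this model as the primary test, keep Fisher's exact test as supportive, and use the same model for conditional power at the looks. Report standardised failure percentages by arm, because the adjusted odds ratio is conditional.
2. In the same edit, state which visits define failure at the final analysis and at the Day 7 looks, including whether Day 1 counts, and settle this before outcome data are seen.
3. State which population the 25/32/38% and 10/15/20% rates describe, and restate power if they exclude subjects on oxygen.

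A worsening-from-baseline endpoint is an option for the sponsor to weigh, not a requested change: it alters the estimand, and its rates would need new justification.

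The cost is one covariate already collected plus wording, with no added visits or subjects and at most about 0.5 points of power when baseline oxygen is not prognostic. If every on-oxygen subject fails, the adjusted estimate comes only from subjects off oxygen at entry, and the report should say so.
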